## **8. MILESTONES**

**Table 1: Study Milestones**

Milestone	Planned Date
Start of data collection	01 March 2016*
End of recruitment	01 March 2020 or until the planned sample size of 128 patients has been enrolled, whichever occurs earlier
End of data collection**	01 March 2021
Data cut-off date for the purposes of interim analysis	When the first enrolled 40 patients complete the 6-month study observation period
Interim report (with results of the interim analysis)	4 months after the data cut-off date for the purposes of interim analysis
Final database lock**	01 June 2021
Final report of study results**	30 September 2021

\* This date corresponds to the actual date of the start of data collection.

\*\* These milestones are subject to change depending on the actual date of the “Last Patient Out”.

## **9. RATIONALE AND BACKGROUND**

### **9.1 MEDICAL BACKGROUND**

The incidence of lung cancer in developed countries is growing. According to 2012 estimates, the age standardized rate of lung cancer (including the trachea and bronchus) was 41.9 per 100,000 cases in Europe, while the respective rate for Greece was 41.6 [1]. Worldwide, lung cancer is the leading cause of cancer-related deaths among males and the second leading cause of cancer-related deaths among women. In Greece, the age-adjusted mortality rates for 2012 were estimated to be 67.7 and 11.8 per 100,000 cases among males and females, respectively [2]. Moreover, despite a wealth of therapies, prognosis of advanced stage non-small cell lung cancer (NSCLC) is poor, with a median overall survival (OS) approaching 10 months with platinum-based chemotherapy and 2 years with targeted therapies [3, 4]. NSCLC is the most common type of lung cancer, and in most cases is diagnosed at an unresectable, locally advanced (stage IIIB) or metastatic stage (IV) [5].

NSCLC bears not only significant mortality, but also morbidity as patients suffer from debilitating symptoms, such as cough, chest pain, dyspnoea, anorexia, fatigue and haemoptysis [4, 6]. Symptoms are at the cornerstone of patients' well-being, as evidenced in a recent survey in which patients reported that prolongation of progression-free survival (PFS) is the most important factor for choosing a treatment only when disease-specific symptoms are mild, while PFS plays a less central role when considering a treatment choice in the presence of severe symptoms. In regards to the specific symptoms, patients ranked fatigue as the most important risk, followed by diarrhoea, nausea and vomiting [7]. In another study, the majority of the subjects (82%) reported that they would prefer supportive therapy alleviating disease-symptoms to chemotherapy, while 68% of those preferring chemotherapy reported that their choice was based on symptom improvement rather than on prolongation of survival [8]. Symptoms affect the patient's physical and emotional well-being and lead to distress not only to the patients but also to their families [9]. Importantly, depression has been considered as an independent prognostic factor in lung cancer cases, regardless of disease severity [10]. A recent study confirmed a positive association between patient-perceived health-related quality of life (HRQoL) after NSCLC treatment initiation and survival [11]. Moreover in another study, baseline HRQoL measured by the European Organisation for Research and Treatment of Cancer (EORTC) Quality of Life Questionnaire Core 30-item [QLQ-C30] emerged as the strongest predictor of OS among advanced NSCLC patients, while the EORTC QLQ-Lung Cancer 13 [EORTC QLQ-LC-13] dyspnoea score was also an independent predictor of OS prolongation [12]. It is thus not surprising that alleviation of symptom burden has been added to the core of disease management, making it imperative to evaluate not only treatment effectiveness but also HRQoL and symptom burden in both clinical research and routine patient care settings [9, 13, 14, 15].

There is a broad array of questionnaires used in the field of NSCLC for the assessment of HRQoL [16]. Among them, the most commonly used generic instruments assessing global health status are the Euro QoL EQ-5D [17] and the cancer-generic EORTC QLQ-C30 [18]. Moreover, disease-specific instruments assessing HRQoL have been developed for patients with NSCLC including the Functional Assessment of Cancer Therapy – Lung (FACT-L) [19], the EORTC QLQ-LC13 [18] and the Lung Cancer Symptom Scale (LCSS) [20]. Euro QoL

EQ-5D is one of the two most frequently used generic questionnaire in lung cancer clinical trials [16].

Apart from the generic and disease-specific tools used for the assessment of HRQoL, the Eastern Cooperative Oncology Group (ECOG) performance status (PS) developed in 1982 [21], has been used in numerous trials as a tool to evaluate how the disease affects the patients' daily living abilities, while its association with effectiveness outcomes is commonly evaluated. In the elderly with advanced NSCLC, ECOG PS was found to be a significant independent factor for OS [22]. Furthermore, in a study of patients with metastatic NSCLC receiving chemotherapy, ECOG PS 2 versus 0 or 1 was found to be associated with a high number of adverse events and poor survival [23].

It is also worthwhile to mention that the World Health Organisation (WHO) cites non-adherence to therapy as a very important, yet modifiable factor of anti-cancer therapy outcomes. Notably among the many factors linked to adherence to oral therapies, are the severity of disease-related symptoms, and the patients' physical and psychological well-being [24] adding further support to the importance of examining symptom and HRQoL outcomes in clinical studies of heavily burdened populations, but also of capturing treatment adherence.

## **9.2 TARGETED THERAPIES FOR NSCLC**

Over the last decade, several targeted therapies have been added in the treatment armamentarium of NSCLC in an attempt to increase efficiency and reduce side effects of other agents. In the treatment of NSCLC, targeted agents have been developed against the vascular endothelial growth factor (VEGF) and the epidermal growth factor receptor (EGFR), and more recently against anaplastic lymphoma kinase (ALK) [25, 26].

For patients with NSCLC tumors harbouring activating mutations of the epidermal growth factor receptor (EGFR), targeted treatments, including the first generation tyrosine kinase inhibitors (TKIs), erlotinib and gefitinib, have shown benefits in terms of prolongation of PFS and increased response rates and improvement of HRQoL [27].

### **9.2.1 Afatinib drug profile**

Resistance to the first-generation EGFR agents therapy commonly develops, which has led to the development of the irreversible EGFR TKI, afatinib, which targets and blocks signalling from dimers of all ErbB family members, EGFR (ErbB1), HER 2 (ErbB2), ErbB3 and ErbB4. Afatinib (GILOTrif®/GIOTrif®) was approved in 2013 by the FDA and EMA based on results of the pivotal phase 3 studies LUX-Lung 3 and LUX-Lung 6. Specifically, in the US afatinib is indicated for the first-line treatment of patients with metastatic NSCLC whose tumors have EGFR exon 19 deletions or exon 21 (L858R) substitution mutations as detected by an FDA-approved test, while in Europe, afatinib as monotherapy is indicated for the treatment of EGFR TKI-naïve adult patients with locally advanced or metastatic NSCLC with activating EGFR mutation(s) [3, 4]. Afatinib is available in orally administered film-coated tablets.

The severity of symptoms and HRQoL when treated with afatinib were examined in the LUX-Lung 1 phase IIb/III randomized controlled clinical trial (RCT), where outcomes of patients treated with afatinib were compared to patients receiving placebo with the use of the EORTC QLQ-C30, the EORTC QLQ-LC13 and the EQ-5D at baseline and every 21 days. Global health as assessed by the EQ-5D as well as global health status, physical functioning

and fatigue assessed by the EORTC QLQ-C30 significantly improved with afatinib treatment. In addition, a significantly higher proportion of patients in the afatinib arm compared to placebo demonstrated improvement in disease-related symptoms, such as cough ( $P<0.0001$ ), dyspnea ( $P=0.006$ ), and pain ( $P<0.0001$ ). In addition, afatinib delayed the time to deterioration of cough ( $P<0.001$ ) [28].

The positive effect of afatinib on symptoms and QoL compared to chemotherapy has been evaluated in the LUX-Lung 3 and LUX-Lung 6 RCTs, where outcomes were assessed using the EORTC QLQ-C30 and LC13 at baseline and every 21 days.

In the LUX-Lung 3 RCT, patients were randomised (2:1) to receive afatinib 40 mg once daily or up to 6 cycles of pemetrexed/cisplatin. According to the results of the study, for the subgroup of patients with common mutations (Del 19, L858R) (204 on afatinib and 104 on chemotherapy) the median PFS was 13.6 versus 6.9 months [Hazard Ratio (HR) 0.47; 95% CI 0.34-0.65;  $P<0.0001$ ] and the median OS was 30.3 versus 26.2 months, demonstrating a clear benefit of afatinib treatment. In addition to the Del 19, L858R mutations, certain less common mutations have also been shown to be sensitive to afatinib treatment [29]. Moreover, compared to chemotherapy first-line afatinib was associated with better control of cough (HR, 0.60; 95% CI, 0.41 to 0.87;  $P=0.007$ ) and dyspnea (HR, 0.68; 95% CI, 0.50 to 0.93;  $P=0.015$ ), as well as improved global health status/QoL ( $P=0.015$ ), and functional scale scores as assessed with the use of EORTC QLQ-C30 and the EORTC-QLQ-L13 [30]. Among the functional scale scores, physical ( $P<0.001$ ), role ( $P=0.004$ ), and cognitive ( $P=0.007$ ) functioning were improved compared to chemotherapy.

The results of the pivotal LUX-Lung 3 RCT have been supported by the LUX-Lung 6 RCT conducted in 36 sites in China, Thailand and South Korea among 364 patients. The study compared first line afatinib with gemcitabine/cisplatin chemotherapy. In the afatinib arm, mean PFS was 11.0 months vs. 5.6 months for those in the chemotherapy arm (HR 0.28;  $P<0.0001$ ). In addition, a significant higher proportion of patients demonstrated improvement of cough ( $P<0.0001$ ), dyspnea ( $P<0.0001$ ) and pain ( $P=0.03$ ), while afatinib also delayed the time to deterioration of these symptoms. Global health improvement was also demonstrated by a higher proportion of patients in the afatinib group than in the gemcitabine and cisplatin group (62·7% versus 32·7%;  $P<0.0001$ ). Notably, prolongation of PFS was associated with improved HRQoL and significantly longer control of disease-related symptoms [3].

Mature survival data from the LUX-Lung 3 and LUX-Lung 6 studies have recently been published. With a median follow-up of 41 months in the LUX-Lung 3, 62% (213/345) patients had died; in the LUX-Lung 6, with a median follow-up of 33 months in the OS rate was 68% (246/364). Among patients treated with afatinib, the median OS was 28.2 months (95% CI, 24.6 to 33.6) in the LUX-Lung 3 and 23.1 months (95% CI, 20.4 to 27.3) in the LUX-Lung 6, which did not significantly differ from the OS in the respective chemotherapy arms. However, OS was significantly longer in the afatinib group (33.3 and 31.4 months in the LUX-Lung 3 and LUX-Lung 6 trials, respectively) than in the chemotherapy group in both trials (21.1 and 18.4 months, in the chemotherapy group of LUX-Lung 3 and LUX-Lung 6, respectively) among patients with Del 19-positive tumors [31].

### **9.3 RATIONALE FOR PERFORMING THE STUDY**

On the ground of the aforementioned evidence, afatinib represents a great advance in the therapeutic armamentarium of advanced NSCLC with activating EGFR mutations. Taking

into consideration the limited real-world evidence that is attributed to the recent advent of afatinib in the market, this field non-interventional study (NIS with new data collection) aims primarily at assessing the impact of the therapy on patients' disease-related symptom burden and HRQoL. These parameters are considered as very important for the evaluation of medicines, especially those aiming to treat complicated diseases that impose a heavy symptom burden, impaired quality of life and poor prognosis, such as NSCLC [9]. Importantly, patients' adherence to this orally administered medication will also be assessed.

In addition, the study represents an attempt towards gaining experience on the routine use of afatinib in daily clinical practice in a representative sample of Greek subjects with advanced NSCLC in real-life clinical settings. The study will complement the evidence available from the RCTs and assist in the decision-making process of the medical professionals that provide care to this heavily burdened population.

## **10. RESEARCH QUESTION AND OBJECTIVES**

### **10.1 PRIMARY OBJECTIVE**

- To evaluate the impact of afatinib therapy on the patient-reported lung cancer-specific symptom burden, using the Average Symptom Burden Index (ASBI) of the LCSS in eligible patients, over 6 months of therapy, in a real world clinical setting in Greece.

### **10.2 SECONDARY OBJECTIVES**

- To evaluate the effect of afatinib therapy on the patient-reported lung cancer-specific symptom burden, total symptomatic distress, functional activity status and global quality of life, using the LCSS total score and domain subscores, at the post-baseline predefined timepoints (*please refer to Section 11.1.2, for the definition of the post baseline timepoints*);
- To assess the impact of afatinib treatment on the HRQoL of the study population using the EQ-5D-3L questionnaire at the post baseline predefined timepoints;
- To assess the impact of afatinib therapy on patient's ECOG PS at the post baseline predefined timepoints;
- To record patient adherence to treatment with afatinib during the study observation period as well as the reasons for missing doses;
- To assess the patterns of use of afatinib in routine clinical practice in terms of treatment modifications (permanent discontinuations, temporary interruptions, dose changes), and reasons for these modifications.

## **11. RESEARCH METHODS**

### **11.1 STUDY DESIGN**

This is a non-interventional, multicentre, cohort study, based on new data collection, which will include a representative sample of patients with advanced/metastatic NSCLC in Greece.

Patients will be treated according to the local prescribing information of the study medication (afatinib, GIOTRIF®) and routine medical practice in terms of visit frequency and types of assessments performed. The assignment of the patient to this therapeutic strategy is not decided in advance by the study protocol but falls within current practice and the prescription of afatinib is clearly separated from the physician's decision to include the patient in the current study.

Since this is purely non-interventional study, primary data -which will be obtained prospectively during the study visits through patients' interview and patient reported outcomes (PROs) or as performed per standard clinical practice- will mainly be employed.

Follow-up visit frequency will be determined by the treating physician, however study-related data will be collected at 2-month ( $\pm 3$  weeks) intervals during the first 12 months of study participation and every 6 months ( $\pm 3$  weeks) thereafter until the end of the study observation period.

The main foreseen limitations for this study are attributed to its observational design and are discussed in the relevant Section [11.10](#). Notably, these limitations are outweighed by the essential role that studies of such design play in evaluating treatment outcomes for marketed products, particularly in heterogeneous patient populations with diseases of complex and heterogeneous biology, such as cancer. The study will provide clinically-relevant real-world data for a broad patient population that will serve as complementary evidence to that of RCTs. In addition, the study outcomes will reflect patient perceptions on symptom burden accounting for variations in local standards of care, treatment patterns and individuals' characteristics.

#### **11.1.1 Synoptic study assessment schedule**

A synoptic study diagram reflecting the assessments of interest and the suggested time schedule is presented in the following figure.

Proprietary confidential information © 2018 Boehringer Ingelheim International GmbH or one or more of its affiliated companies

[figure not shown]

Figure 1: Synoptic Study Diagram

### **11.1.2 Baseline and post-baseline timepoint definitions**

In the context of this study the following definitions apply for the baseline and post-baseline assessments:

- **Baseline assessments** are defined as the assessments performed prior to or at afatinib treatment onset. For PROs (patient-reported LCSS and EQ-5D-3L), the scores that will be collected at the enrolment visit will serve as the baseline data.
- **Post-baseline predefined timepoints** for study-specific assessments are defined as: every 2 months ( $\pm$  3 weeks) during the first 12 months of therapy and every 6 months ( $\pm$  3 weeks) thereafter until the end of patient's participation in the study.

### **11.1.3 Study primary and secondary endpoints**

#### **11.1.3.1 Primary endpoint/outcome measure**

- 6-month symptom improvement rate using the LCSS ASBI, i.e., proportion of patients who will experience a minimum clinically important improvement in symptoms (*defined as a decrease in the ASBI from enrolment  $\geq$ 10 in two consecutive assessments*) over 6 months of treatment.

Note: A patient will be categorized as having:

- an **improved ASBI** if the mean of any two consecutive post-baseline ASBI assessments for that patient is at least 10 points below the patient's ASBI at enrolment;
- a **worsened ASBI** if the mean of any two consecutive post-baseline ASBI assessments for that patient is at least 10 points above the value at enrolment;
- a **stable ASBI** if the mean of any two consecutive post-baseline ASBI assessments for that patient is within 10 points of the value at enrolment.

[figure not shown]
A change of 10 points on a 0-100 scale is considered sufficient to indicate a clinically meaningful change [32, 33, 34]; this magnitude is about the same as the 0.5 standard deviation that has also reported as a universally acceptable minimum clinically important difference [35].

[figure not shown]

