Study design:	
This is a non-interventional, multicentre, cohort study, based on new data collection, which will include a representative sample of patients with advanced/metastatic NSCLC in Greece.
 
Patients will be treated according to the local prescribing information of the study medication (afatinib, GIOTRIF®) and routine medical practice in terms of visit frequency and types of assessments performed. Since this is purely non-interventional study, primary data obtained prospectively during the study visits through patients' interview and patient reported outcomes (PROs) or as performed per standard clinical practice will mainly be employed.
 
The overall study duration period is expected to be 60 months, including a 48-month enrollment period and a minimum 12-month follow-up period. During the observation period, data will be collected at routine clinical visits at 2-month intervals for the first 12 months and at 6-month intervals thereafter until the end of study participation. The end of study participation is defined as a maximum of 48 months after afatinib treatment initiation or disease progression, death, withdrawal of consent, unacceptable toxicity, study completion or physician's decision whichever occurs earlier. The maximum 48-month length of participation in the study pertains to the patients enrolled during the first 12 months of recruitment, while the maximum observation period for the last patient enrolled is 12 months.

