### **11.8.2 Analysis for the primary endpoint**

Pertaining to the primary endpoint the proportion of patients experiencing a minimum clinically important symptom improvement (*as defined in Section 11.1.3.1*) over a 6-month period of treatment will be calculated along with the respective 95% confidence interval; in addition the relevant proportions of patients whose symptom burden has remained stable and deteriorated will be calculated. The 95% confidence interval will be derived from Wald confidence limits for a binomial proportion.

In order to examine the impact of baseline characteristics including among others, gender, age, BMI, educational/marital/employment status, disease stage, histological subtype, sites of metastases, EGFR mutation subtype, smoking status and smoking history, ECOG PS, type of concomitant medications and comorbidities, as well as adherence to therapy at 6 months on the study primary endpoint, a binary logistic regression model will be applied.

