## Statistical Analysis Plan

### 2.1 Study objectives and endpoints

#### 2.1.1 Primary objective and endpoint

The primary objective of the study is:

- To evaluate the impact of afatinib therapy on the patient-reported lung cancer-specific symptom burden, using the Average Symptom Burden Index (ASBI) of LCSS in eligible patients, over 6 months of therapy, in a real world clinical setting in Greece.

The primary endpoint of the present study is:

- 6-month symptom improvement rate using the LCSS ASBI, i.e., proportion of patients who will experience a minimum clinically important improvement in symptoms (defined as a decrease in the ASBI from enrolment  $\geq 10$  in two consecutive assessments) over 6 months of treatment.

*Note: A patient will be categorized as having:*

- ✓ *an improved ASBI if the mean of any two consecutive post-baseline ASBI assessments for that patient is at least 10 points below the patient's ASBI at enrolment;*
- ✓ *a worsened ASBI if the mean of any two consecutive post-baseline ASBI assessments for that patient is at least 10 points above the value at enrolment;*
- ✓ *a stable ASBI if the mean of any two consecutive post-baseline ASBI assessments for that patient is within 10 points of the value at enrolment.*

*A change of 10 points on a 0-100 scale is considered sufficient to indicate a clinically meaningful change; this magnitude is about the same as the 0.5 standard deviation that has also reported as a universally acceptable minimum clinically important difference.*

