### 4.2 Handling of dropouts or missing data

With regard to partial start dates with a missing start day, e.g. \_ \_ JUN2016, the day will be set to the first of the month, 01JUN2016. If the month is missing e.g. 17 \_ \_ 2016, the month will be set to January for that year, 17JAN2016. The reverse will apply for a partial end date, with the missing day set to the end of the month and the missing month set to December. If there is only a year and both the day and month are missing, then both are imputed, giving 1st January for a start date or 31st December for a stop date. In case where a partial date after the general imputation rule comes in reasonable opposition with another variable of the eCRF, then the date will be imputed so as to be in reasonable time sequence.

In the context of the final analysis, regarding the primary outcome measure, in case of a high non-evaluable rate (i.e. >20%) the primary endpoint analysis will also be conducted in the subset of patients with at least one post-baseline measurement of the ASBI score. Details about this analysis are presented in Section 8.1.3.

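### 'Worsened' needs two consecutive scores but progression ends participation, so deterioration first recorded at the exit visit is undercounted and partly shown as 'stable'

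*Protocol*

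**What the plan says.** Protocol 11.1.3.1 sorts patients into improved, worsened and stable by the mean of two consecutive post-baseline ASBI (Average Symptom Burden Index) scores compared with enrolment. A patient is worsened "if the mean of any two consecutive post-baseline ASBI assessments for that patient is at least 10 points above the value at enrolment". SAP 2.1.1 repeats the three definitions without an exception for a last assessment. The 10-point limit is justified in the same protocol section: "A change of 10 points on a 0-100 scale is considered sufficient to indicate a clinically meaningful change".

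The assessments for the primary endpoint are enrolment and months 2, 4 and 6 (Protocol 11.4.1; SAP 2.2.1.1). A patient therefore has at most two consecutive post-baseline pairs.

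Follow-up stops at clinical failure: "The end of study participation is defined as a maximum of 48 months after afatinib treatment initiation or disease progression, death, withdrawal of consent", with unacceptable toxicity also listed (Protocol Abstract, Study design; SAP 2.3). SAP 3.3 keeps scores taken at premature withdrawal only if they fall within the predefined time points.

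On reporting, Protocol 11.8.2 gives the improvement proportion with its confidence interval, and "in addition the relevant proportions of patients whose symptom burden has remained stable and deteriorated will be calculated". The primary analysis uses the Per Protocol Set (PPS), which requires available primary-endpoint data (Protocol 11.8.1; SAP 3.5). If more than 20% are non-evaluable, SAP 4.2 adds that "the primary endpoint analysis will also be conducted in the subset of patients with at least one post-baseline measurement of the ASBI score". It refers to Section 8.1.3 for details, and that section is not in the text available for this review.

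**The concern.** The wording treats improvement and worsening alike, but follow-up does not. A patient who improves usually stays and has a next visit at which the change can be confirmed. A patient whose symptoms worsen with progression or toxicity leaves, so the event being measured removes its own confirming visit. The exit score can only be paired with an earlier score that may predate the deterioration.

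This would hold even if every exit questionnaire were completed in window and kept. Readers will set the improved, stable and deteriorated proportions side by side. If patients who left after a rise of 10 points or more appear as 'stable', or drop out of the table, the balance looks more favourable to treatment than the scores show.

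**Working it through.** **The plan's own figure.** The plan gives no expected deteriorated share. Its sample size concerns the improvement proportion and reproduces: SE = √(0.25/96) = 0.0510, half-width 1.96 × 0.0510 = 0.100, relative SE 0.0510/0.5 = 10.2%, and 96/0.75 = 128. Nothing below changes it.

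**Exact part, with no assumptions.** Let d be the change from enrolment at the preceding visit and x the change at exit. 'Worsened' requires (d + x)/2 ≥ 10, so x ≥ 20 − d.

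| Preceding change d | Rise needed at exit |
|---|---|
| −10 | 30 |
| −5 | 25 |
| 0 | 20 |
| +5 | 15 |
| +9 | 11 |
| +10 | 10 |

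With one post-baseline score there is no pair, so no rise qualifies. A mean of at least 10 needs at least one score of 10 or more. The rule can therefore never count more worsened patients than a single-visit 10-point criterion would.

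**Illustrative size.** The inputs are:
- SD 20, because the protocol says of the 10 points that "this magnitude is about the same as the 0.5 standard deviation".
- Correlation 0.75 between assessments (assumed). The SD of a change is then 20 × √(2 × 0.25) = 14.1.
- Mean change before exit 0 or −5, with an exit rise of 10, 15 or 20 points added to it (assumed).
- Exponential time to progression with medians 11.0 and 13.6 months. Both figures are in Protocol 9.2.1, which calls the 11.0 a mean.
- The exit score replaces the next scheduled visit and always counts (assumed).

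Exits by month 6 are 1 − 2^(−6/11.0) = 31.5% and 1 − 2^(−6/13.6) = 26.3%. Exits before month 2, which leave no pair, are 11.8% and 9.7%. Exits between months 2 and 6 are 19.6% and 16.7%.

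The chance of an exit score at least 10 above enrolment is P(Z ≥ (10 − m)/14.1), where m is the mean exit change. The share of paired patients labelled 'worsened' comes from simulation. Four of the twelve scenarios, in % of the cohort unless stated:

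| Median; mean change before exit; rise | P(exit ≥ 10) | No pair | Has pair | Paired and labelled worsened (% of pairs) | Missed by averaging | Missed in all |
|---|---|---|---|---|---|---|
| 13.6; −5; 10 | 0.36 | 3.5 | 6.0 | 53% | 2.8 | 6.3 |
| 11.0; 0; 10 | 0.50 | 5.9 | 9.8 | 64% | 3.5 | 9.5 |
| 11.0; −5; 20 | 0.64 | 7.6 | 12.5 | 53% | 5.9 | 13.5 |
| 11.0; 0; 20 | 0.76 | 9.0 | 14.9 | 65% | 5.2 | 14.2 |

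(Totals may differ in the last digit through rounding.) For the second row: 0.118 × 0.50 = 5.9%, 0.196 × 0.50 = 9.8%, and 9.8% × (1 − 0.64) = 3.5%.

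Over all twelve scenarios, 6 to 14% of the cohort leave with a rise of at least 10 and are not called worsened. Averaging accounts for about 3 to 6 points (4 to 8 of 128 patients). The absence of a pair accounts for about 3.5 to 9 points (4 to 12 of 128). If the exit rise is instead measured from enrolment, the total is 8 to 16 points, of which averaging gives 3 to 7.

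**The case against.** The strongest defence is that two-visit averaging is a deliberate requirement for sustained change, stated for the mean and applied equally in both directions. It guards against noise. With a change SD of 14.1, a patient with no true change shows a rise of 10 or more at a single visit with probability P(Z ≥ 10/14.1) = 24%. This stands. It is the reason not to redefine 'worsened' by one score while 'improved' keeps confirmation.

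Confirmation also fails for improvement at month 6, the last visit in the primary window. Under the same assumptions about 7 to 8% of completers, or 5 to 6% of the cohort, have a fall of at least 10 at month 6 without being 'improved'. That is as large as the averaging effect above, so the claim that improvement always gets confirmed is too strong. However, month-6 truncation also affects worsening in patients who stay, whereas exit for clinical failure falls mainly on worsening.

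Other limits also stand. SAP Section 8 is not visible and may deal with single-score patients. SAP 6.2 allows progression to be identified by imaging or laboratory criteria, so not every progression brings a symptom rise. Deterioration is also visible elsewhere: ASBI change by visit (Protocol 11.8.3), withdrawals with reasons (SAP 5.1) and progression by visit (SAP 6.2). None of these corrects the label of a patient who has a pair and leaves worse.

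A reader might infer that exit worsening always needs twice the stated threshold, or that the plan contradicts its own 10-point limit. Neither follows. Twenty points applies only when the preceding score equals enrolment, and the limit is defined for the two-visit mean.

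**Conclusion.** The concern holds for the deteriorated share. The formula 20 − d, the exclusion of single-score patients and the downward direction relative to a 10-point rise at exit follow from the documents alone. No visible text repairs the label for patients who have a pair.

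The size does not follow from the documents. The 3 to 6 points from averaging rest on the assumed SD, correlation, exit rise and shape of progression-free survival. The 3.5 to 9 points without a pair are a missing-data matter, because those patients probably fall outside the PPS. Quoting the combined 6 to 14 points as the effect of the averaging rule would overstate it.

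A reader might also infer that the primary improvement rate is inflated by this rule. The documents do not support that. A rise at exit does not enter the improvement numerator, and the stable and deteriorated proportions accompany the primary endpoint in a descriptive single-arm study. The change is worth making because the three shares will be read together and 'stable' is a misleading label for a patient who left with a clinically meaningful rise.

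**What to change.** Leave the three confirmed categories and their common two-assessment rule unchanged. In Protocol 11.8.2 and the corresponding SAP text, add a separate row, 'unconfirmed worsening at exit'. It covers patients not already confirmed as worsened whose last available ASBI is at least 10 above enrolment and whose participation ended for progression, toxicity or death before a further assessment.

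- Do not count these patients as 'stable'.
- Include those with a single post-baseline score.
- Use the Full Analysis Set as denominator, and show the three categories on that denominator too so that the rows can be read together.
- If a patient met 'improved' on an earlier pair, keep that label and footnote the overlap.
- State whether an exit score outside a visit window counts for this row, given SAP 3.3.

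The cost is one definition and one programming condition on data already collected. The downside is noise: at the 24% single-visit rate shown above, some of these patients will have had no true change. The row should therefore be labelled supportive and not merged with confirmed worsening.
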